#### **14.3.5 Displays of Other Laboratory, Vital Signs, Electrocardiogram, Physical Examination, and Other Safety Data**

- Table 14.3.5.1 Clinical Laboratory Summary – Serum Chemistry (Safety Population)
- Table 14.3.5.2 Clinical Laboratory Change from Baseline – Serum Chemistry (Safety Population)
- Table 14.3.5.3 Clinical Laboratory Shift from Baseline – Serum Chemistry (Safety Population)
- Table 14.3.5.4 Clinical Laboratory Summary – Hematology (Safety Population)
- Table 14.3.5.5 Clinical Laboratory Change from Baseline – Hematology (Safety Population)
- Table 14.3.5.6 Clinical Laboratory Shift from Baseline – Hematology (Safety Population)
- Table 14.3.5.7 Clinical Laboratory Summary – Coagulation (Safety Population)
- Table 14.3.5.8 Clinical Laboratory Change from Baseline – Coagulation (Safety Population)
- Table 14.3.5.9 Clinical Laboratory Fold Change from Baseline – Activated Partial Thromboplastin Time (Safety Population)
- Table 14.3.5.10 Clinical Laboratory Shift from Baseline – Coagulation (Safety Population)
- Table 14.3.5.11 Clinical Laboratory Summary - Urinalysis (Safety Population)
- Table 14.3.5.12 Clinical Laboratory Change from Baseline – Urinalysis (Safety Population)
- Table 14.3.5.13 Clinical Laboratory Shift from Baseline – Urinalysis (Safety Population)

Table 14.3.5.14 Vital Sign Summary (Safety Population)

Table 14.3.5.15 Vital Sign Change from Baseline (Safety Population)

Table 14.3.5.16 12-Lead Electrocardiogram Summary (Safety Population)

Table 14.3.5.17 12-Lead Electrocardiogram Change from Baseline (Safety Population)

### **10.3 Section 16 Data Listings**

**Note:** Hepatitis and HIV results that are provided by the clinical laboratory will not be presented in subject data listings and will not be included in any database transfer.

Data listings are numbered following the ICH structure but may be renumbered as appropriate during the compilation of the TFLs for the CSR. The following is a list of appendix numbers and titles that will be included as data listings:

#### **16.1 Study Information**

Appendix 16.1.9 Statistical Methods

Appendix 16.1.10.1 Clinical Laboratory Reference Ranges

#### **16.2 Subject Data Listings**

##### **16.2.1 Subject Discontinuation**

Appendix 16.2.1 Subject Discontinuation (Safety Population)

##### **16.2.2 Protocol Deviations**

Appendix 16.2.2 Protocol Deviations

##### **16.2.3 Subjects Excluded from Pharmacodynamic Analysis**

Appendix 16.2.3 Subjects Excluded from  
Pharmacodynamic/Immunogenicity Analysis

Note: Appendices 16.2.2 and 16.2.3 are generated in MS Word for inclusion in the study report.

##### **16.2.4 Demographic Data**

Appendix 16.2.4.1 Demographics (Safety Population)

Appendix 16.2.4.2 Physical Examination (Safety Population)

Appendix 16.2.4.3 Medical and Surgical History (Safety Population)

Appendix 16.2.4.4 Substance Use (Safety Population)

## **16.2.5 Compliance and/or Drug Concentration Data**

- Appendix 16.2.5.1.1 Inclusion Criteria
- Appendix 16.2.5.1.2 Exclusion Criteria
- Appendix 16.2.5.2 Subject Eligibility (Safety Population)
- Appendix 16.2.5.3.1 Check-in and Return Criteria
- Appendix 16.2.5.3.2 Check-in Criteria and Responses (Safety Population)
- Appendix 16.2.5.4.1 Test Compound Description
- Appendix 16.2.5.4.2 Test Compound Administration Times (Safety Population)
- Appendix 16.2.5.5 Blood Draw Times (Safety Population)
- Appendix 16.2.5.6 Meal Times (Safety Population)
- Appendix 16.2.5.7 Prior and Concomitant Medications (Safety Population)

## **16.2.6 Individual Efficacy/Pharmacokinetic/Pharmacodynamic Response Data**

- Appendix 16.2.6.1 Individual Plasma APC-PCI Levels Versus Time Following Administration of a Single IV Dose of 0.5, 1.0, 2.0, 4.0 mcg/kg, or Placebo (Linear Scale) for <Subject #>
- Appendix 16.2.6.2 Plasma Anti-E-WE Thrombin Antibodies

## **16.2.7 Adverse Events Listings**

- Appendix 16.2.7.1.1 Adverse Events (I of II) (Safety Population)
- Appendix 16.2.7.1.2 Adverse Events (II of II) (Safety Population)
- Appendix 16.2.7.2 Adverse Event Related Procedure (Safety Population)
- Appendix 16.2.7.3 Adverse Event Preferred Term Classification (Safety Population)

## **16.2.8 Listings of Individual Laboratory Measurements and Other Safety Observations**

- Appendix 16.2.8.1.1 Clinical Laboratory Report - Serum Chemistry (Safety Population)
- Appendix 16.2.8.1.2 Clinical Laboratory Report - Hematology (Safety Population)
- Appendix 16.2.8.1.3 Clinical Laboratory Report - Coagulation (Safety Population)
- Appendix 16.2.8.1.4 Clinical Laboratory Report - Urinalysis (Safety Population)

- Appendix 16.2.8.1.5 Clinical Laboratory Report - Urine Drug Screening (Safety Population)
- Appendix 16.2.8.1.6 Clinical Laboratory Report - Comments (Safety Population)
- Appendix 16.2.8.2 Vital Signs (Safety Population)
- Appendix 16.2.8.3 12-Lead Electrocardiogram (Safety Population)

## **11. TABLE AND FIGURE SHELLS**

The following table shells provide a framework for the display of data from this study. The shells may change due to unforeseen circumstances. These shells may not be reflective of every aspect of this study, but are intended to show the general layout of the tables that will be presented and included in the final CSR. Unless otherwise noted, all tables will be presented in Times New Roman font size 8. These tables will be generated off of the Celerion ADaM Version 2.1.

### 11.1 In-text Summary Tables Shells

Table 10-1 Subject Disposition Summary (Safety Population)

Disposition	Dose Level				Pooled Placebo	Overall
	0.5 mcg/kg	1.0 mcg/kg	2.0 mcg/kg	4.0 mcg/kg		
Dosed	XX (XX%)	XX (XX%)	XX (XX%)	XX (XX%)	XX (XX%)	XX (XX%)
Completed	XX (XX%)	XX (XX%)	XX (XX%)	XX (XX%)	XX (XX%)	XX (XX%)
Discontinued	X (XX%)	X (XX%)	X (XX%)	X (XX%)	X (XX%)	X (XX%)
<Reason1>	X (XX%)	X (XX%)	X (XX%)	X (XX%)	X (XX%)	X (XX%)
<Reason2>	X (XX%)	X (XX%)	X (XX%)	X (XX%)	X (XX%)	X (XX%)
0.5 mcg/kg: 0.5 mcg/kg E-WE thrombin (IV bolus) 1.0 mcg/kg: 1.0 mcg/kg E-WE thrombin (IV bolus) 2.0 mcg/kg: 2.0 mcg/kg E-WE thrombin (IV bolus) 4.0 mcg/kg: 4.0 mcg/kg E-WE thrombin (IV bolus) Pooled Placebo: Placebo Solution (IV bolus) <AE = Adverse event>  Source: Table 14.1.1 Program: /CAXXXXXX/sas_prg/thsas/intext/t_disp.sas DDMMYYYY HH:MM						

Table 11-1 Demographic Summary (Safety Population)

Trait	Category/ Statistics	Dose Level				Pooled Placebo	Overall
		0.5 mcg/kg	1.0 mcg/kg	2.0 mcg/kg	4.0 mcg/kg		
Sex	Female	XX (XX%)	XX (XX%)	XX (XX%)	XX (XX%)	XX (XX%)	XX (XX%)
Race	Asian	XX (XX%)	XX (XX%)	XX (XX%)	XX (XX%)	XX (XX%)	XX (XX%)
	Black or African American	XX (XX%)	XX (XX%)	XX (XX%)	XX (XX%)	XX (XX%)	XX (XX%)
	White	XX (XX%)	XX (XX%)	XX (XX%)	XX (XX%)	XX (XX%)	XX (XX%)
Ethnicity	Hispanic or Latino	XX (XX%)	XX (XX%)	XX (XX%)	XX (XX%)	XX (XX%)	XX (XX%)
	Not Hispanic or Latino	XX (XX%)	XX (XX%)	XX (XX%)	XX (XX%)	XX (XX%)	XX (XX%)
Age* (yrs)	n	XX	XX	XX	XX	XX	XX
	Mean	XX.X	XX.X	XX.X	XX.X	XX.X	XX.X
	SD	X.XX	X.XX	X.XX	X.XX	X.XX	X.XX
	Minimum	XX	XX	XX	XX	XX	XX
	Median	XX.X	XX.X	XX.X	XX.X	XX.X	XX.X
	Maximum	XX	XX	XX	XX	XX	XX
Weight (kg)	n	XX	XX	XX	XX	XX	XX
	Mean	XX.X	XX.X	XX.X	XX.X	XX.X	XX.X
	SD	X.XX	X.XX	X.XX	X.XX	X.XX	X.XX
	Minimum	XX	XX	XX	XX	XX	XX
	Median	XX.X	XX.X	XX.X	XX.X	XX.X	XX.X
	Maximum	XX	XX	XX	XX	XX	XX
0.5 mcg/kg: 0.5 mcg/kg E-WE thrombin (IV bolus) 1.0 mcg/kg: 1.0 mcg/kg E-WE thrombin (IV bolus) 2.0 mcg/kg: 2.0 mcg/kg E-WE thrombin (IV bolus) 4.0 mcg/kg: 4.0 mcg/kg E-WE thrombin (IV bolus) Pooled Placebo: Placebo Solution (IV bolus) *Age is calculated at the time of first dosing. BMI = Body mass index  Source: Table 14.1.2 Program: /CAXXXXX/sas_prg/stsas/intexttest/t_dem.sas DDMMYY HH:MM							

**Programmer Notes:**

- This is just a mock table shell. Please use the race categories listed in the CRF.
- Height (cm) and BMI (kg/m^2) will be also summarized in this table.

In-text Table 11-2 will be in the following format.

Table 11-2 Summary of APC-PCI Following Administration of a Single IV Dose of 0.5, 1.0, 2.0, and 4.0 mcg/kg E-WE Thrombin

Hour	0.5 mcg/kg (N=X)	1.0 mcg/kg (N=X)	2.0 mcg/kg (N=X)	4.0 mcg/kg (N=X)	Placebo (N=X)
XX	X ± X	X ± X	X ± X	X ± X	X ± X
XX	X ± X	X ± X	X ± X	X ± X	X ± X
XX	X ± X	X ± X	X ± X	X ± X	X ± X
XX	X ± X	X ± X	X ± X	X ± X	X ± X

N is the total number of subjects dosed at each dose level.  
Source: Table XXX

Treatments:

- 0.5 mcg/kg E-WE thrombin (IV bolus)
- 1.0 mcg/kg E-WE thrombin (IV bolus)
- 2.0 mcg/kg E-WE thrombin (IV bolus)
- 4.0 mcg/kg E-WE thrombin (IV bolus)
- Pooled Placebo (IV bolus)

Programmer's note:

- Arithmetic mean ± SD will be presented.
- Table 11-2 the source table will be 14.2.1.1 through 14.2.1.5.

In-text Tables 11-3 and 11-4 will be in the following format.

Table 11-3 Summary of Anti- E-WE Thrombin Plasma ADA Following Administration of a Single IV Dose of 0.5, 1.0, 2.0, and 4.0 mcg/kg E-WE Thrombin

	0.5 mcg/kg (n=x)	1.0 mcg/kg (n=x)	2.0 mcg/kg (n=x)	4.0 mcg/kg (n=x)	Placebo (n=x)
Predose (Day -1)					
ADA Test Result Number Negative/Positive	X/X	X/X	X/X	X/X	X/X
Confirmatory E-WE Thrombin Positive	X	X	X	X	X
Neutralizing Positive	X	X	X	X	X
Day 14					
ADA Test Result Number Negative/Positive	X/X	X/X	X/X	X/X	X/X
Confirmatory E-WE Thrombin Positive	X	X	X	X	X
Neutralizing Positive	X	X	X	X	X
Day 28					
ADA Test Result Number Negative/Positive	X/X	X/X	X/X	X/X	X/X
Confirmatory E-WE Thrombin Positive	X	X	X	X	X
Neutralizing Positive	X	X	X	X	X

Presentation of Data:

- The following outcomes will be presented as number of subjects (% of the population): confirmatory positive will be a percentage of the total subject in the dose level
- Number of subjects will be presented as an integer (no decimals)
- 4 dose levels will be presented instead on the same table
- Internal Table template: Table ITPar1

Programmer's note:

- Table 11-3 the source table will be 14.2.2.1.
- Table 11-4 the source table will be 14.2.2.2.
- ADA collection times: Predose, Day 14 and Day 28 postdose.

Program: /CAXXXXX/sas\_prg/pksas/intext-pk-tables.sas DDMMYYYY HH:MM  
Program: /CAXXXXX/sas\_prg/pksas/adam\_intext\_pkparam.sas DDMMYYYY HH:MM

Table 12-1 Treatment-Emergent Adverse Event Frequency by Cohort - Number of Subjects Reporting the Event (% of Subjects Dosed) (Safety Population)

Adverse Event*	Dose Level				Pooled Placebo	Overall
	0.5 mcg/kg	1.0 mcg/kg	2.0 mcg/kg	4.0 mcg/kg		
Number of Subjects With TEAEs	XX (XX%)	XX (XX%)	XX (XX%)	XX (XX%)	XX (XX%)	XX (XX%)
Number of Subjects Without TEAEs	XX (XX%)	XX (XX%)	XX (XX%)	XX (XX%)	XX (XX%)	XX (XX%)
System Organ Class 1	X (X%)	X (X%)	X (X%)	X (X%)	X (X%)	X (X%)
Preferred Term 1	X (X%)	X (X%)	X (X%)	X (X%)	X (X%)	X (X%)
Preferred Term 2	X (X%)	X (X%)	X (X%)	X (X%)	X (X%)	X (X%)
System Organ Class 2	X (X%)	X (X%)	X (X%)	X (X%)	X (X%)	X (X%)
Preferred Term 1	X (X%)	X (X%)	X (X%)	X (X%)	X (X%)	X (X%)
Preferred Term 2	X (X%)	X (X%)	X (X%)	X (X%)	X (X%)	X (X%)
0.5 mcg/kg: 0.5 mcg/kg E-WE thrombin (IV bolus) 1.0 mcg/kg: 1.0 mcg/kg E-WE thrombin (IV bolus) 2.0 mcg/kg: 2.0 mcg/kg E-WE thrombin (IV bolus) 4.0 mcg/kg: 4.0 mcg/kg E-WE thrombin (IV bolus) Pooled Placebo: Placebo Solution (IV bolus) *Adverse events are classified according to MedDRA Version 21.0. TEAEs = Treatment-emergent adverse events If a subject has 2 or more clinical adverse events, the subject is counted only once within a category. The same subject may appear in different categories.  Source: Table 14.3.1.1 Program: /CAXXXXX/sas prg/stsas/intext/t ae.sas DDMMYYYY HH:MM						

## 11.2 Section 14 Summary Tables Shells

Part 1 of X

Table 14.1.1 Subject Disposition Summary (Safety Population)

Disposition	Dose Level				Pooled Placebo	Overall
	0.5 mcg/kg	1.0 mcg/kg	2.0 mcg/kg	4.0 mcg/kg		
Dosed	X (XX%)	X (XX%)	X (XX%)	X (XX%)	X (XX%)	X (XX%)
Completed	X (XX%)	X (XX%)	X (XX%)	X (XX%)	X (XX%)	X (XX%)
Discontinued	X (XX%)	X (XX%)	X (XX%)	X (XX%)	X (XX%)	X (XX%)
<Reason 1>	X (XX%)	X (XX%)	X (XX%)	X (XX%)	X (XX%)	X (XX%)
<Reason 2>	X (XX%)	X (XX%)	X (XX%)	X (XX%)	X (XX%)	X (XX%)

Note: 0.5 mcg/kg: 0.5 mcg/kg E-WE thrombin (IV bolus)  
 1.0 mcg/kg: 1.0 mcg/kg E-WE thrombin (IV bolus)  
 2.0 mcg/kg: 2.0 mcg/kg E-WE thrombin (IV bolus)  
 4.0 mcg/kg: 4.0 mcg/kg E-WE thrombin (IV bolus)  
 Pooled Placebo: Placebo Solution (IV bolus)

Program: /CAXXXXX/sas\_prg/stsas/tab PROGRAMNAME.sas DDMMYYYY HH:MM

Table 14.1.2 Demographic Summary (Safety Population)

Trait	Category/ Statistics	Dose Level				Pooled Placebo	Overall
		0.5 mcg/kg	1.0 mcg/kg	2.0 mcg/kg	4.0 mcg/kg		
Sex	Female	X ( XX%)	X ( XX%)	X ( XX%)	X ( XX%)	X (XX%)	X (XX%)
Race	Asian	X ( XX%)	X ( XX%)	X ( XX%)	X ( XX%)	X (XX%)	X (XX%)
	Black or African American	X ( XX%)	X ( XX%)	X ( XX%)	X ( XX%)	X (XX%)	X (XX%)
	White	X ( XX%)	X ( XX%)	X ( XX%)	X ( XX%)	X (XX%)	X (XX%)
Ethnicity	Hispanic or Latino	X ( XX%)	X ( XX%)	X ( XX%)	X ( XX%)	X (XX%)	X (XX%)
	Not Hispanic or Latino	X ( XX%)	X ( XX%)	X ( XX%)	X ( XX%)	X (XX%)	X (XX%)
Age* (yrs)	n	X	X	X	X	X	X
	Mean	XX.X	XX.X	XX.X	XX.X	XX.X	XX.X
	SD	X.XX	X.XX	X.XX	X.XX	X.XX	X.XX
	Minimum	XX	XX	XX	XX	XX	XX
	Median	XX.X	XX.X	XX.X	XX.X	XX.X	XX.X
	Maximum	XX	XX	XX	XX	XX	XX
Weight (kg)	n	X	X	X	X	X	X
	Mean	XX.X	XX.X	XX.X	XX.X	XX.X	XX.X
	SD	X.XX	X.XX	X.XX	X.XX	X.XX	X.XX
	Minimum	XX	XX	XX	XX	XX	XX
	Median	XX.X	XX.X	XX.X	XX.X	XX.X	XX.X
	Maximum	XX	XX	XX	XX	XX	XX

Programmer Note: This is just a mock table shell. Please use the race categories listed in the CRF.  
Please also include Height (cm) and BMI (kg/m2).

Note: 0.5 mcg/kg: 0.5 mcg/kg E-WE thrombin (IV bolus)  
1.0 mcg/kg: 1.0 mcg/kg E-WE thrombin (IV bolus)  
2.0 mcg/kg: 2.0 mcg/kg E-WE thrombin (IV bolus)  
4.0 mcg/kg: 4.0 mcg/kg E-WE thrombin (IV bolus)  
Pooled Placebo: Placebo Solution (IV bolus)  
\*Age is calculated at the time of first dosing.

Program: /CAXXXXX/sas\_prg/stsas/tab PROGRAMNAME.sas DDMMYYYY HH:MM

**Tables 14.2.1.1 through 14.2.1.5 will be in the following format:**

Table 14.2.1.1 Plasma APC-PCI Levels (<units>) Following a Single IV Dose of 0.5 mcg/kg E-WE Thrombin (Pharmacodynamic Population)

Subject Number	Sample Times (hr)				
	Pre-dose	Hour X	Hour X	Hour X	Hour X
XXX	XXX	XXX	XXX	XXX	XXX
XXX	XXX	XXX	XXX	XXX	XXX
XXX	XXX	XXX	XXX	XXX	XXX
XXX	XXX	XXX	XXX	XXX	XXX
XXX	XXX	XXX	XXX	XXX	XXX
XXX	XXX	XXX	XXX	XXX	XXX
n	X	X	X	X	X
Mean	X.XX	X.XX	X.XX	X.XX	X.XX
SD	X.XX	X.XX	X.XX	X.XX	X.XX
CV (%)	X.XX	X.XX	X.XX	X.XX	X.XX
Minimum	X.XX	X.XX	X.XX	X.XX	X.XX
Median	X.XX	X.XX	X.XX	X.XX	X.XX
Maximum	X.XX	X.XX	X.XX	X.XX	X.XX

. = Value missing or not reportable.

Programmer Notes:

- PD time points for the 3 PD markers are presented in Sections 6.1 through 6.3 of the SAP
- Verify Section 6.4 for presentation of descriptive statistics.

Program: /AAXXXXX/ECR/sas prg/pksas/PROGRAMNAME.sas DDMMYYYY HH:MM

**Tables 14.2.2.1 and 14.2.2.2 will be in the following format.**

Table 14.2.2.1 Plasma Anti-E-WE Thrombin Antibody Detection Following Administration of a Single IV Dose of 0.5, 1.0, 2.0, or 4.0 mcg/kg E-WE Thrombin Summary by Collection Time and Treatment - Number of Subjects (% Total Subjects)

Test	Result	0.5 mcg/kg				1.0 mcg/kg			
		Day X	Day X	Day X	Overall*	Day X	Day X	Day X	Overall*
		N=X	N=X	N=X	N = X	N=X	N=X	N=X	N = X
Initial	Negative	X (X%)	X (X%)	X (X%)	X (X%)	X (X%)	X (X%)	X (X%)	X (X%)
	Positive	X (X%)	X (X%)	X (X%)	X (X%)	X (X%)	X (X%)	X (X%)	X (X%)
Confirmatory	Negative	X (X%)	X (X%)	X (X%)	X (X%)	X (X%)	X (X%)	X (X%)	X (X%)
	Positive	X (X%)	X (X%)	X (X%)	X (X%)	X (X%)	X (X%)	X (X%)	X (X%)
Neutralizing	Negative	X (X%)	X (X%)	X (X%)	X (X%)	X (X%)	X (X%)	X (X%)	X (X%)
	Positive	X (X%)	X (X%)	X (X%)	X (X%)	X (X%)	X (X%)	X (X%)	X (X%)

N is the total number of subjects dosed at each dose level.

Programmer Note:

- Immunogenicity sampling times: Day -1, Day 14, and Day 28
- Treatments:
  - 0.5 mcg/kg E-WE thrombin (IV bolus)
  - 1.0 mcg/kg E-WE thrombin (IV bolus)
  - 2.0 mcg/kg E-WE thrombin (IV bolus)
  - 4.0 mcg/kg E-WE thrombin (IV bolus)
  - Pooled Placebo: Placebo Solution (IV bolus)

Note: \* if the response of a subject is positive at least once postdose, it will be counted as "positive"; otherwise will be considered as "negative".

Only screening positives will be reassayed for confirmatory analysis.

Program: /AAXXXXX/ECR/sas\_prg/pksas PROGRAMNAME.sas DDMMYYYY HH:MM

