- j If thrombin time and/or aPTT are found to be elevated at Day 14, both tests will be repeated. If aPTT and/or thrombin time are elevated beyond the normal range (unless it is still within  $\pm 10\%$  of individual's baseline value at check-in) in the retest, a mixing study will be performed. The mixing study will be performed on Day 14 by mixing the subjects' plasma 1:1 with normal human pooled plasma. aPTT and thrombin time will be evaluated. If the aPTT and/or thrombin time do not correct to normal range, the presence of ADA cross-reacting prothrombin/thrombin antibodies will be presumed. The applicable subject will remain at the CRU until

these test results are obtained. Subjects for whom aPTT and/or thrombin time did not reach  $\pm 10\%$  of the baseline value or within the normal range by Day 14, will return every 7 days ( $\pm 2$  days) until aPTT and thrombin time reach  $\pm 10\%$  of the baseline value or within the normal range.

- k Subjects in the sentinel group (Cohort 1 only) will be dosed at least 28 days prior to remaining subjects. The remaining subjects in Cohort 1 and subjects in the Cohorts 2, 3, and 4 will be dosed in two groups separated by at least 14 days. Dosing in each group will be staggered by at least 1 hour.
- l: Immunogenicity testing for ADA will be first performed on blood samples taken on Days 14 and 28. If ADA are found, the check-in sample of ADA will be evaluated.

Abbreviations: ADA = Anti-drug antibodies, AE = Adverse event, APC-PCI = Activated protein C with protein C inhibitor, aPTT = Activated partial thromboplastin time, C-I = Check-in, Chem = Chemistry, CRU = Clinical research unit, FSH = Follicle-stimulating hormone, FU = Follow-up, Hem = Hematology, HIV = Human immunodeficiency virus, INR = International normalized ratio, PD = Pharmacodynamic, PI = Principal Investigator, PT = Prothrombin time, Scr = Screening, UA = Urinalysis.

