## 10. INVESTIGATIONAL PLAN

### 10.1 Overall Study Design and Plan

This is a randomized, double-blind, placebo-controlled, SAD study conducted at one study center in the US.

Four (4) cohorts of either 6 subjects (Cohort 1 [4 active and 2 placebo]) or 5 subjects (Cohorts 2, 3, and 4 [4 active and 1 placebo]) are planned for evaluation.

In each cohort, subjects will receive a single IV bolus of E-WE thrombin or placebo. Subjects will participate in only 1 cohort.

Cohort 1 will contain a sentinel group of 2 subjects (1 placebo and 1 active) who will be dosed at least 28 days before the remaining group of subjects. The remaining subjects in Cohort 1, and subjects in each of Cohorts 2, 3, and 4 will be dosed in 2 groups separated by at least 14 days (2 subjects in each group [Cohort 1] or 2 subjects in the first group and 3 subjects in the second group [Cohorts 2-4]). The placebo will be randomized to either group.

Dose escalation to the next dose level (i.e., next cohort) will be determined as per [Section 10.4.1.4](#). See [Section 10.4.1.2](#) for dose levels in each cohort. Subjects will participate in only one cohort. An attempt will be made to have at least 30% of the total subjects of a race/ethnicity minority group. An attempt will be made to include at least 2 females per cohort.

Safety (i.e., physical examinations, vital signs, ECGs, clinical laboratory tests [including coagulation], thrombin time, immunogenicity, injection site reaction, and AEs) will be assessed throughout the study.

Blood samples will be collected for PD assessment (i.e., APC-PCI) of E-WE thrombin at scheduled time points listed in the Study Events Flow Chart ([Section 6](#)) predose and for 24 hours postdose.

If ADA are found at the time of follow-up on Day 14 and/or Day 28, the check-in sample of ADA will be evaluated.

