## **10.3 Selection of Study Population**

### **10.3.1 Number of Subjects**

The study is planned to enroll up to 21 subjects in 4 cohorts [i.e., dose levels] with 6 subjects in Cohort 1 [4 subjects randomized to receive the active drug and 2 subjects to receive the placebo] and 5 subjects in Cohorts 2, 3, and 4 [4 subjects randomized to receive the active drug and 1 subject to receive the placebo]. In each cohort, an attempt will be made to have at least 30% of the subjects be of a race/ethnicity minority group. An attempt will be made to include at least 2 females in each cohort.

Cohort 1 will contain a sentinel group of 2 subjects (1 placebo and 1 active). The sentinel group will be dosed at least 28 days before the remaining subjects in Cohort 1. The remaining subjects in the cohort will be dosed after evaluation of the sentinel subjects' Day 28 safety data and will be dosed in 2 groups separated by at least 14 days (2 subjects in the first group and 2 subjects in the second group). The placebo will be randomized to either group.

The Cohorts 2, 3, and 4 will be dosed in 2 groups separated by at least 14 days (2 subjects in the first group and 3 subjects in the second group). The placebo will be randomized to either group.

Additional subjects (up to 6 subjects per cohort) may be enrolled if it is deemed appropriate by the PI and the Sponsor to repeat a dose level or to study an intermediate dose level (lower than those planned) in a new cohort of subjects.

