## **7. IMMUNOGENICITY**

Plasma and serum samples for immunogenicity testing will be collected on Days -1, 14, and 28. If ADA are detected on Days 14 and 28, the check-in sample on Day -1 will be also evaluated. ADA detection will be reported and summarized.

Assessment of ADA will be performed by Haemtech Biopharma Services, Inc.

For samples with a positive confirmatory assay, titers of ADA will be presented with the same level of precision as received from the bioanalytical laboratory. A table will be provided for ADA positive duration for each dose level, where duration is defined

as the time interval between the first postdose and last postdose occurrence of positive ADA.

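### The ADA tables give Day -1 percentages out of all subjects dosed, although the check-in sample is assayed only after post-dose antibody has been found

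*SAP*

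**What the plan says.** **Testing rule.** Footnote l of the protocol's Study Events Flow Chart sets the order: "Immunogenicity testing for ADA will be first performed on blood samples taken on Days 14 and 28". Protocol section 10.1 gives the trigger for the baseline sample: "If ADA are found at the time of follow-up on Day 14 and/or Day 28, the check-in sample of ADA will be evaluated". SAP section 7 words it differently: "If ADA are detected on Days 14 and 28, the check-in sample on Day -1 will be also evaluated".

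**Reporting rule, Section 14 tables.** The programmer note to SAP Tables 14.2.2.1 and 14.2.2.2 reads "Immunogenicity sampling times: Day -1, Day 14, and Day 28". Each day is a column with its own N and with Negative and Positive rows for the initial, confirmatory and neutralizing tests. The table title expresses the counts as percentages of total subjects. The denominator is defined beneath: "N is the total number of subjects dosed at each dose level".

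**Reporting rule, in-text tables.** Tables 11-3 and 11-4 carry a predose (Day -1) block whose first line is "ADA Test Result Number Negative/Positive", given as raw counts under a lower-case n that the shell does not define. Percentages are specified for the confirmatory result: "confirmatory positive will be a percentage of the total subject in the dose level".

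**Planned size.** Protocol section 10.3.1: "The study is planned to enroll up to 21 subjects in 4 cohorts".

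**The concern.** The shells treat Day -1 like the other two visits, as if every dosed subject had a result. Under the testing rule, a subject with no post-dose ADA has no Day -1 result. The shells have no category for such a subject and no rule for scoring one. A programmer following the note must either leave untested subjects out of both rows, so that the percentages do not add up to the stated N, or count them as negative without an assay.

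What is at stake is how the Day -1 figures are read. A predose entry out of all subjects dosed looks like the prevalence of antibody before treatment. Here it would come only from subjects selected because they were positive afterwards.

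**Working it through.** **1. Planned numbers.** Active: 4 + 4 + 4 + 4 = 16. Placebo: 2 + 1 + 1 + 1 = 5. Total: 16 + 5 = 21, which agrees with protocol section 10.3.1. The SAP pools the placebo subjects, so the table groups are four of size 4 and one of size 5.

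**2. How many have a Day -1 result.** Let k be the number of subjects in a group who meet the trigger for the check-in assay. Read per subject, k have a Day -1 result and N - k do not. For an active dose level with N = 4, the share of N that Negative plus Positive can cover is k/4:

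| k | With a Day -1 result | Without | (Negative + Positive)/N |
|---|---|---|---|
| 0 | 0 | 4 | 0% |
| 1 | 1 | 3 | 25% |
| 2 | 2 | 2 | 50% |
| 3 | 3 | 1 | 75% |
| 4 | 4 | 0 | 100% |

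The stated denominator is right only when all four subjects have post-dose ADA. With no post-dose ADA anywhere, 0 of 21 subjects have a Day -1 result.

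**3. Example.** Take one post-dose positive in a dose level of 4, whose check-in sample is also positive. On N = dosed, the Day -1 column shows Positive 1/4 = 25%. The other 3/4 = 75% are unknown. If they are entered as negative, the column shows 75% negative with no assay behind it. On the number assayed, the result is 1/1.

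**4. Likely extent over the trial.** The documents give no ADA rate, so I assume a rate p of 5% to 50% in active subjects and none on placebo. The expected number without a Day -1 result is 21 - 16p. The probability that an active dose level of 4 has no Day -1 result at all is (1 - p)^4.

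| p | 21 - 16p | (1 - p)^4 |
|---|---|---|
| 5% | 20.2 | 0.815 |
| 10% | 19.4 | 0.656 |
| 20% | 17.8 | 0.410 |
| 30% | 16.2 | 0.240 |
| 50% | 13.0 | 0.0625 |

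Across this range, more than half of the 21 subjects are expected to have no Day -1 score.

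**5. Trigger wording.** The protocol tests the check-in sample after ADA on either follow-up day or both. Read literally, the SAP requires both days, so a subject positive on one day only would not be tested. The SAP reading can therefore only leave k the same or make it smaller.

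**6. Whether another rule rescues the shell.** The reduced-denominator rule in SAP section 8 names laboratory, ECG and vital-sign data, not ADA. The default to negative in Tables 14.2.2.1 and 14.2.2.2 is marked for the Overall column and concerns post-dose results. Neither reaches Day -1.

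**The case against.** **The per-subject trigger is an inference.** Neither document says that the check-in sample is tested in positive subjects only, and a study-wide trigger is not excluded. This stands as a caution. If one positive led to assay of every check-in sample, N = dosed would then be correct. With no post-dose ADA, though, the whole Day -1 column would still be empty, so the shell fails in a foreseeable case on either reading.

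**The shells are provisional.** SAP section 11 says that they may change and show only the general layout. That lowers the importance of the point. It does not remove it, because the definition of N is an explicit rule and not a placeholder.

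**The gap would be visible.** If untested subjects are simply left out, a shortfall against N = 4 is easy to see. A listing of plasma anti-E-WE antibodies is also planned (Appendix 16.2.6.2). This helps in part; the SAP's list of appendices names no matching serum anti-WT listing.

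**In-text tables.** Tables 11-3 and 11-4 give Negative/Positive as raw counts, so the denominator error does not arise on that line. It does arise for the confirmatory percentage, and the counts still need a statement of how many subjects were tested.

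**Stronger readings.** A reader might infer that the baseline for judging the Day 14 and Day 28 rates is wrong. The documents plan no such comparison: the Overall column and ADA duration use post-dose results only, and the stopping rule refers to the presence of ADA, not to change from baseline. A reader might also infer that the predose data are invalid. They are not: under the protocol's trigger, each post-dose positive subject has a Day -1 result that can be read individually.

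**Conclusion.** The Day -1 percentages in Tables 14.2.2.1 and 14.2.2.2, and the predose confirmatory percentage in Tables 11-3 and 11-4, are on a denominator that the testing rule does not support. In an active dose level, Day -1 Negative plus Positive falls short of N unless all four subjects have post-dose ADA. The Day -1 figures must not be read as the prevalence of pre-existing antibody.

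This rests on the per-subject reading of the trigger. The table over ADA rates in the working is illustrative, because the rates are assumed; the k/4 result does not depend on them.

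The Day 14 and Day 28 initial-test results, the Overall column, ADA duration, the stopping rule and the adverse event endpoints are not affected. This is a minor reporting correction.

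**What to change.** In the four shells (Tables 11-3, 11-4, 14.2.2.1 and 14.2.2.2), for Day -1 only:

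- use the number of subjects with an assayed Day -1 sample as the denominator, and show that number;
- add a 'Not tested' row;
- add a footnote stating when the Day -1 sample is assayed. It is needed even with the corrected denominator, because the tested subjects are selected on their post-dose result.

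Before writing the footnote, reconcile the trigger between protocol section 10.1 and SAP section 7, and state whether it applies per subject.

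The cost is a change to the shells, a denominator and some wording, with no new data. Assaying every stored Day -1 sample would make N = dosed correct for subjects with a sample, at up to 21 x 2 = 42 initial assays plus confirmation of any positives. That is optional and not needed for the fix.
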